#### **4.4.2.4 Eosinophilic esophagitis quality of life score**

Summary statistics for the EoE quality of life score at baseline, end of the double-blind treatment, and end of the open-label treatment will be reported for each treatment group and overall. The changes in quality of life score from baseline to end of the double-blind treatment and to end of the open-label treatment as well as the Hodges-

Lehmann estimates along with 95% CIs for difference of medians of these changes between the two treatment groups will be reported (*Table 14*).

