In addition, the change from baseline to end of treatment of the total symptom score and individual symptom scores (Abdominal/chest pain score, Vomiting score, and Dysphagia score) will be generated by treatment group and overall. The comparison of the change of individual symptom scores between the two treatment groups will be evaluated by using Fisher's exact tests.

The responses will be divided into three categories as suggested: Poor <30% improvement, good 30-70% improvement and excellent >70% improvement from baseline.

Percentage of subjects per response rate

The percentage of subjects showing an excellent response (≤ 1 eos/HPF), good response (2-14 eos/HPF), or poor response (≥ 15 eos/HPF) at the end of treatment will also be presented and analyzed between the two treatment groups using Fisher's exact test.

Eosinophilic Esophagitis Quality of Life Score

The Quality of Life score will also be reported for each treatment group at baseline and the end of treatment. The change from baseline to end of treatment will also be presented. The change in QOL scores between two treatment groups will be compared with two-sample t-test or Mann-Whitney test depending on the distribution of the change of the QOL score.

Combination Score:

Combination Score of four measures (Eosinophils/HPF, EREFS, investigator assessment and parental assessment of symptoms) will be calculated at baseline, end of treatment and end of study. The combination score will be calculated as (maximum eosinophils per high power field) + [10*esophageal endoscopy score (EREFs)] + [2* Parent assessment of esophageal symptoms (PEESS)] + [5*investigator assessment of EoE symptom activity]. The change from baseline to end of treatment will also be presented. The change in QOL scores between two treatment groups will be compared with two-sample t-test or Mann-Whitney test depending on the distribution of the change of the QOL score.

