## **4. Statistical Analyses**

This section provides a detailed description of the statistical analyses and methods, tables, listings, and figures. SAP Table shells are presented in Section 5.1.

The definitions of the analysis populations are listed. The general description of the planned analysis is provided. Descriptive and baseline characteristics will be generated for the purpose of describing the study population. Because the sample size is small, sometimes the most informative way of presenting the data will be through graphs or listing of the raw data.

The primary and secondary efficacy endpoints will be analyzed using the intent-to-treat (ITT) and per protocol populations. The least squares mean and two-sided 95% confidence interval (CI) for the between-treatment differences will be estimated from the models. The Hodges-Lehmann analysis of median differences will be produced for some of the secondary efficacy endpoints. Relative risk (RR) or odds ratio (OR) with 95% CI will be presented for some of the binary endpoints. Longitudinal models will be used to analyze some of the efficacy endpoints. These models will focus on the difference between baseline and end of the double-blind treatment as well as end of

the open-label treatment; measurements taken before the end of the double-blinded treatment will be used to increase the precision of the estimates of the changes from baseline to the both end of the double-blind treatment and the end of the open-label treatment. Sensitivity analyses will be performed to examine the potential outliers and influential points. These measurements will be assessed by visual examination of histograms and normal probability plots of residuals from the models. The methods or statistical tests that will be used in the primary and secondary efficacy analyses and safety analyses are described. Details are provided below.

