##### **4.4.2.1 Total esophageal endoscopy score**

The total score for each subject will be calculated and summary statistics at baseline, end of the double-blind treatment, and end of the open-label treatment as well as the changes from baseline to end of the double-blind treatment and to end of the open-label treatment will be presented by treatment groups (*Table 8*). Hodges-Lehmann estimate with 95% CI for difference of median of the changes in esophageal endoscopy

scores between two treatment groups will be reported. The total score at the end of the double-blind treatment and at the end of the open-label treatment between two treatment groups will be analyzed separately using ANCOVA as described in Section 4.4.1. The least square means for the treatment groups, difference in least square means between the treatment groups, and a two-sided 95% CI for the difference between the treatment groups will be presented (*Table 9*).

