#### **4.4.2.2 Eosinophilic esophagitis symptom and global assessment scores**

Summary statistics for individual eosinophilic esophagitis symptom score (Abdominal/Chest pain, Vomiting/Regurgitation, and Dysphagia) as well as investigator's eosinophilic esophagitis global assessment score at baseline, end of the double-blind treatment, and end of the open-label treatment as well as changes from baseline to end of the double-blind treatment and to end of the open-label treatment will be presented by treatment groups and overall (*Table 10*). The total EoE symptom score for each subject will be calculated and summary statistics at baseline, end of the double-blind treatment, and end of the open-label treatment, as well as the changes from baseline to end of the double-blind treatment and to end of the open-label treatment will be presented by treatment groups and overall. Improvement in symptom scores will be defined as a decrease in total eosinophilic esophagitis symptom score of two or more from baseline to end of the double-blind treatment and to end of the open-label treatment. Subjects will be categorized based on whether they improved their symptoms in two different ways. First, subjects who improved their symptom scores are considered as responders and subjects who did not improve their symptom scores are considered as non-responders. Second, subjects who improved their symptom scores will be categorized as poor improvement (<30%), good improvement (30-70%), and excellent improvement (>70%). RR or OR along with 95%

CI for the percentage of responders between two treatment groups will be presented. (*Table 11*).

In addition, frequency and severity EoE symptom scores measured by Pediatric Eosinophilic Esophagitis Symptoms Score (PEESS) will be examined. Summary statistics for the frequency and severity EoE symptom scores at baseline, end of the double-blind treatment, and end of the open-label treatment will be reported for each treatment group and overall. The changes in frequency and severity EoE symptom scores from baseline to end of the double-blind treatment and to end of the open-label treatment will be reported and Hodges-Lehmann estimates with 95% CIs for differences of medians of these changes between two treatment groups will be reported (*Table 12*).

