#### **4.4.2.5 Composite score**

Summary statistics for the composite score at baseline, end of the double-blind treatment, and end of the open-label treatment will be reported for each treatment group and overall. The changes in composite score from baseline to end of the double-blind treatment and to end of the open-label treatment as well as the Hodges-Lehmann estimates along with 95% CIs for differences of medians of these changes between the two treatment groups will be reported (*Table 15*).

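### Quality of life, PEESS and the composite are compared only on unadjusted change from baseline; a baseline-adjusted Visit 10 comparison should be added and the baseline visit named

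*SAP*

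**What the plan says.** - **Quality of life** (SAP 4.4.2.4, Table 14): "The changes in quality of life score from baseline to end of the double-blind treatment and to end of the open-label treatment" are summarised, with Hodges-Lehmann differences and 95% CIs.
- **PEESS** (SAP 4.4.2.2, Table 12): "Hodges-Lehmann estimates with 95% CIs for differences of medians of these changes between two treatment groups will be reported".
- **Composite** (SAP 4.4.2.5, Table 15): "The changes in composite score from baseline to end of the double-blind treatment", and likewise to the end of open-label treatment, with Hodges-Lehmann "estimates along with 95% CIs for differences of medians of these changes between the two treatment groups will be reported".
- **Protocol 13.6.4.2**: "The change in QOL scores between two treatment groups will be compared with two-sample t-test or Mann-Whitney test". The same sentence, still worded for quality of life, stands under the combination score.
- **Endoscopy score** (SAP 4.4.2.1, Tables 8 and 9): Hodges-Lehmann on change and, in addition, the Visit 10 and Visit 16 totals "will be analyzed separately using ANCOVA as described in Section 4.4.1", that is, with the baseline value as covariate.
- **General statement** (SAP 4): "Longitudinal models will be used to analyze some of the efficacy endpoints". No endpoint is named, and no shell for the three scores shows such a model.

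**The concern.** A change score is a baseline adjustment with the slope fixed at 1. If the true slope is lower, subtracting the baseline adds noise and over-corrects any chance baseline difference between arms. With only 6 placebo children, such differences will often be sizeable. Protocol 6.3 names quality of life as one of two key endpoints, and Protocol 13.2 and SAP 3.2 expect the pilot data to feed a power analysis for a larger study. A needlessly imprecise estimate would therefore carry forward. The SAP already holds the remedy, because it adjusts the endoscopy score for baseline, and it gives no reason for leaving these three scores out.

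**Working it through.** **Inputs.** Arm sizes are 16 and 6 (SAP 2.4.2); SAP 3.2 has 15 and 5. Neither document gives a precision, power, SD or correlation for these scores, so there is no plan figure to reproduce. The correlation rho between baseline and follow-up, and the SD ratio k = SD(baseline)/SD(follow-up), are assumptions and are varied below.

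**1. Equal SDs (k = 1), normal data.** In units of the follow-up variance s²:
- Var(change) = 2(1−rho)s²
- Var(ANCOVA) = (1−rho²)s²
- ratio = (1+rho)/2, so the information lost by raw change is (1−rho)/2

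Estimating the slope multiplies the ANCOVA variance by 1 + 1/(N−4), which is 1 + 1/18 = 1.056 at N = 22. The ratio of CI widths is √[(1+rho)/2 × 1.056], times a factor close to 1 for 19 rather than 20 degrees of freedom. The fourth column is a simulation of the planned Hodges-Lehmann estimate on change against ANCOVA (20,000 normal data sets, 16 versus 6).

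| rho | loss (1−rho)/2 | after covariate cost | simulated Hodges-Lehmann | ANCOVA CI narrower by |
|---|---|---|---|---|
| 0 | 50% | 47% | 51% | 27% |
| 0.3 | 35% | 31% | 37% | 17% |
| 0.5 | 25% | 21% | 26% | 11% |
| 0.6 | 20% | 16% | not run | 8% |
| 0.7 | 15% | 10% | 16% | 5% |
| 0.8 | 10% | 5% | 11% | 2% |

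At 15 versus 5 the simulated losses are nearly the same (50%, 35%, 26%, 16% and 12% at rho 0, 0.3, 0.5, 0.7 and 0.8).

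**2. Unequal SDs.** Loss = 1 − (1−rho²)/(1 + k² − 2k·rho), before the covariate cost:

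| k | rho 0 | rho 0.3 | rho 0.5 |
|---|---|---|---|
| 0.25 | 6% | 0.3% | 8% |
| 0.5 | 20% | 4% | 0% |
| 1.25 | 61% | 50% | 43% |

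This matters for the composite. If its baseline is the milk-free biopsy, eligibility holds the eosinophil component to 0–10 per HPF, so its SD is at most 5. The planned SD after milk is 20 (SAP 3.2), so k is at most 5/20 = 0.25 for that component. The SDs of the other components are not given.

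**3. Chance imbalance.** The SD of the baseline difference between arms is √(1/16 + 1/6) = 0.48 baseline SD. With equal SDs, raw change leaves (1−rho) times the realised difference uncorrected. For a one-SD difference that is 0.7 × 0.48 = 0.34 SD at rho 0.3 and 0.5 × 0.48 = 0.24 SD at rho 0.5.

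**4. Non-normal data.** Simulated variance of ANCOVA divided by variance of Hodges-Lehmann on change, 16 versus 6; above 1 favours the planned estimate:

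| distribution | rho 0.3 | rho 0.5 | rho 0.8 |
|---|---|---|---|
| normal | 0.63 | 0.74 | 0.89 |
| lognormal, log-SD 0.7 (rho on log scale) | 1.01 | 1.17 | 1.42 |
| lognormal, log-SD 1 (rho on log scale) | 1.67 | 1.96 | 2.38 |
| heavy-tailed (t, 3 df) | 0.91 | 1.06 | 1.26 |

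A baseline-adjusted Hodges-Lehmann estimate (the shift in the Visit 10 value minus the fitted slope times baseline) had 0.45 to 0.96 of the variance of the planned estimate in the cases tried.

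**5. Which baseline.** Protocol Tables 3A and 3B schedule quality of life at V2 (on milk), V3 (milk-free), V10 and V16, and not on Day 1. PEESS is listed with the quality-of-life instruments in Appendix 2. SAP 4.4.2.2, 4.4.2.4 and 4.4.2.5 do not say which screening value is the baseline, and both rho and k depend on that choice.

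**The case against.** **Hodges-Lehmann is a sound choice for small, possibly skewed samples.** This stands in part. Step 4 shows that ordinary ANCOVA can be less precise than the planned estimate under skew or heavy tails. The composite contains a raw maximum eosinophil count, for which SAP 4.4.1 itself foresees a log scale. However, robustness to outliers does not correct baseline imbalance, and a baseline-adjusted robust estimate keeps both properties.

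**The SAP is consistent: change endpoints get Hodges-Lehmann, level endpoints get ANCOVA.** SAP 2.2.4 does define quality of life and the composite only as changes, and the endoscopy score as both level and change. A reader might infer that the SAP contradicts itself. It does not for those two scores; only PEESS has a level endpoint without ANCOVA. Adjustment still fits a change endpoint, because regressing change on treatment and baseline gives the same treatment coefficient as regressing the Visit 10 value on them.

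**The longitudinal models in SAP 4 may cover this.** They name no endpoint. The extra precision they promise comes from measurements before the end of double-blind treatment, and quality of life has no on-treatment measurement before Visit 10.

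**The numbers are assumed.** This stands. A reader might infer that a quarter to a half of the precision is certainly lost. That needs rho of 0.5 or less, equal SDs and roughly normal data, none of which is in the documents. If V2 is the baseline, it shares a diet state with Visit 10, and rho may be higher.

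**These are secondary endpoints in a pilot.** This is true, and it limits the weight of the point. The primary analysis is untouched.

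**Conclusion.** The point holds with a qualified size. For the three scores, the only between-arm estimate specified in the SAP is unadjusted change. With equal SDs and near-normal data this loses (1−rho)/2 of the information before a covariate cost of about 6% of variance: 25–50% for rho 0–0.5 and 10–20% for rho 0.6–0.8. Confidence intervals change less, by about 11% at rho 0.5 and 2% at rho 0.8. The loss may be close to nil if the baseline SD is well below the follow-up SD, as is likely for the composite with a milk-free baseline, and larger if baseline varies more.

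A reader might also infer that the planned estimates are biased. Randomisation keeps the change-score comparison unbiased on average; what remains is imprecision and sensitivity to whichever imbalance occurs. The change is worth making because it uses data the trial already collects and a model the SAP already contains.

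**What to change.** 1. In SAP 4.4.2.2 (PEESS), 4.4.2.4 and 4.4.2.5, add a Visit 10 comparison: ANCOVA of the Visit 10 value on treatment and that score's baseline, as in 4.4.2.1. Report the LS-mean difference with 95% CI in Tables 12, 14 and 15, and keep the Hodges-Lehmann estimate alongside.
2. State which screening visit, V2 or V3, is the baseline for each score. Because clinical care decides the order of the screening endoscopies, name the diet state as well.
3. For a skewed or heavy-tailed score, notably the composite, specify in advance a log scale or a rank-based or baseline-adjusted Hodges-Lehmann version.
4. Align Protocol 13.6.4.2, and reword its combination-score paragraph so that it refers to that score.

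Cost: a few sentences, one more column in three tables and about one degree of freedom. No new data are needed.

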#### **4.4.2.5 Composite score**

Summary statistics for the composite score at baseline, end of the double-blind treatment, and end of the open-label treatment will be reported for each treatment group and overall. The changes in composite score from baseline to end of the double-blind treatment and to end of the open-label treatment as well as the Hodges-Lehmann estimates along with 95% CIs for differences of medians of these changes between the two treatment groups will be reported (*Table 15*).

#### **4.4.2.6 Development of symptoms**

Time to development of symptoms after milk reintroduction at month 9 and 20 will be described across two treatment groups.

#### **4.4.2.7 Exploratory biologic markers**

The Hodges-Lehmann estimates for median differences for continuous variables and RRs for categorical variables along with 95% CIs of the changes in exploratory biologic markers, including T-regulatory cells, TSLP, CBC with differential, and milk-specific immunoglobulin level, as well as epigenetic changes between the active treatment group and the placebo group will be reported.

### **4.5 Safety analysis**

AEs, laboratory tests (hematology and chemistry), and vital signs will be listed. No formal statistical analysis of safety endpoints will be performed. The details of the safety analysis are provided below.

#### **4.5.1 Adverse events**

All AEs will be listed/described and reported by treatment groups, subject, start date, severity, grade, causality, action taken, stop date, outcome, and absence of serious AE (*Table 16A and Table 16B*). All AEs will be coded by system organ class and preferred term using the Medical Dictionary for Regulatory Activities (MedDRA). The number of subjects who experienced at least one AE as well as the number of AEs will be summarized by system organ class and treatment group (*Table 17A and Table 17B*). The Summary of AEs (total number of subjects with AEs, total number of AEs, number of AEs per subject, severity of AEs, any serious AEs, AEs leading to discontinuation and death, ongoing AEs, and outcome) by treatment group will be presented (*Table 18*). TEAEs will be defined as any AEs, regardless of relationship to study drug, which occur during the AE collection period of study drug or any event already present that worsens in either intensity or relationship to study drug following exposure to the Viaskin® Milk. TEAE will be considered drug-related if relationship information is missing. An overall summary of TEAEs (the number and percentage of subjects with any TEAE, total number of subjects with potentially drug-related TEAE, total number of TEAEs, total number of local TEAE, number of TEAEs per subject, severity of TEAEs, any serious TEAE, any TEAE leading to discontinuation and death) by treatment groups will be provided (*Table 19A and Table 19B*). The number of subjects with adverse events on local skin reactions will be summarized (Table 20)

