The time of application and removal of each Viaskin® will be noted on the subject diary cards (see Section 10.10), along with any observed AE(s) (local and/or distant). Application of the Viaskin® at a similar time for each application (am or pm) is recommended.

After Visit 10, all subjects will continue treatment with open-label Viaskin® Milk 500 µg for up to 11 additional months. It is permitted at the discretion of the Investigator, to postpone the application of the first patch up to a maximum of 7 days after V10.

To increase the safety of subjects at the beginning of the open-label treatment period, in particular for subjects crossing over from placebo to the active Viaskin Milk treatment, the daily duration of application will again be adapted from Visit 10 for the first weeks of treatment: 6 hours/day during the first week, 12 hours/day during the second week, and for an entire 24 hours daily from the third week onwards. During the period of 24 hours of daily application, flexibility of 24 hours ± 4 hours of daily application is permitted.

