8.5.4 Blinding of Study Medication

This is a randomized, double-blind, placebo-controlled study with limited access to the randomization code. Active and placebo Viaskin® will be similar in physical appearance. The treatment each subject will receive will not be disclosed to the Investigator, study center personnel, subject, Sponsor or their representatives. The treatment codes will be held according to the interactive Web response system (IWRS).

The second phase of the study will be on open-label extension with all patients receiving unblinded Active Viaskin® milk patch. There will be no blinding of study medication during this part of the study.

For details of the emergency procedure for unblinding of individual subjects, see Section 8.5.10, below.

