12. SAFETY MEASUREMENTS AND VARIABLES

12.1 Adverse Events Definition

An AE is any untoward medical occurrence that does not necessarily have a causal relationship with the investigational medicinal product. An AE can therefore be any unfavorable or unintended sign, including an abnormal laboratory finding, symptom or disease temporally associated with the use of an investigational medicinal product whether or not considered related to the investigational medicinal product.

AEs will be monitored throughout the entire study. Investigators will ask the subject at each visit if they have experienced any untoward effects since the last study visit. All AEs will be recorded on the eCRFs provided. A description of the event, severity, time of occurrence, duration, any action

(e.g. treatment and follow up tests) and the outcome should be provided along with the Investigator's assessment of the relationship to the study treatment.

AEs will be recorded from the time written screening informed consent is signed until the time of the End of Study visit. AEs still ongoing at the time of End of study visit will be followed for an additional period to encompass a total period of 14 days of AE follow-up after administration of the last dose of treatment.

If known, the name or diagnosis of the illness should be recorded, rather than a listing of individual signs or symptoms. AEs must be graded as being mild, moderate or severe and their start and end dates given. Definitions of severity are as follows:

- Mild:** an AE usually transient in nature and generally not interfering with normal activities
- Moderate:** an AE that is sufficiently discomforting to interfere with normal activities;
- Severe:** an AE that is incapacitating and prevents normal activities.

Even if the Investigator feels there is no relationship to the study drug, all adverse experiences MUST be recorded in the eCRF. The Investigator is requested to assess the relationship of any clinical adverse experience to treatment using the following definitions:

Unrelated: those AEs which are clearly and incontrovertibly due to extraneous causes (concurrent drugs, environment etc.) and do not meet the criteria for drug relationship listed under Unlikely, Possible, Probable or Related.

Unlikely: an adverse experience may be considered unlikely if it includes at least the first two features:

- It does not follow a reasonable temporal sequence from administration of the drug.

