Appendix 3: CHOP Monitoring Policy

Introduction:

Description of the study:

This is a double-blind, placebo-controlled, randomized trial to study the efficacy and safety of Viaskin® Milk, an allergen extract of milk administered epicutaneously using the Viaskin® epicutaneous delivery system in subjects from 4 to 17 years old with a milk induced Eosinophilic Esophagitis. The trial will be conducted at The Children's Hospital of Philadelphia (CHOP).

Study objectives:

The objectives of this study are:

- To assess the efficacy of Viaskin® Milk epicutaneous immunotherapy (EPIT) in subjects with milk-induced eosinophilic esophagitis.
- To evaluate the safety of Viaskin® Milk EPIT in subjects with milk-induced eosinophilic esophagitis.

Critical data and study procedures, with particular attention to data and procedures that are unusual in relation to clinical routine and require training of study site staff

Specific risks to be addressed by monitoring:

Upper Endoscopy and biopsy-Pain or bleeding

Viaskin Patch-local skin reactions, any systematic reaction to Viaskin patch including rash, vomiting, abdominal pain or other GI symptoms

Treatment-emergent AEs (TEAEs) will be defined as any AEs, regardless of relationship to study drug, which occur during or after the initial Viaskin® application of study drug or any event already present that worsens in either intensity or relationship to study drug following exposure to the Viaskin®. If relationship information is missing, the TEAE will be considered drug-related.

Description of Monitoring Approaches

The Office of Research Compliance (ORC) will begin monitoring activities for this study within three months of the first subject's enrollment into the study. Thereafter, ORC will monitor this study annually unless circumstances necessitate more frequent monitoring, e.g., an increase in risk to the subjects, less than ideal study conduct, higher than expected accrual rates.

Monitoring activities will be guided by ICH E6 section 5.18.

Monitoring of subject data will be initiated at 100% verification of the data recorded. This may be amended, and a tapered approach to monitoring may be employed, if conduct and documentation of the study reaches a level of reliability that would permit valid conclusions based upon a sampling of data.

Communication of Monitoring Results

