#### 4.1 Analysis populations

The analysis populations are:

- **Safety population:** The safety population is comprised of all subjects who are randomized and received at least one dose of study treatment and all subjects in the control group who did not withdraw or were not withdrawn. This population will be used to assess comparative safety information.
- **Intent-to-treat population:** The intent-to-treat (ITT) population (full analysis set) is comprised of all subjects who are randomized. Subjects in the ITT population will be categorized by their randomized treatment assignment. This population will be used to assess comparative efficacy information.
- **Per protocol population:** The per protocol (PP) population includes all subjects in the ITT population who do not have pre-defined major deviations from the protocol that may affect the primary (and secondary) endpoints (i.e., subjects who have not gone through the third upper endoscopy and biopsy at the end of the double-blind treatment, subjects with a compliance below 80%, etc.). The PP population will be used to perform confirmatory analyses of the primary efficacy evaluation.

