Table 19A. Treatment-Emergent AEs (TEAEs)\* by Treatment Groups  
(Number of subjects (%))

	All	Viaskin® milk	Placebo
TEAEs			
Potentially drug-related TEAE			
Severity of TEAE			
Mild			
Moderate			
Severe			
Life-threatening			
Death			
Serious TEAE			
TEAE leading to discontinuation			
TEAE leading to death			
Number of TEAEs			
0			
1			
2			
3 +			
Ongoing			
Yes			
No			
Outcome			
Unchanged			
Worsened			
Recovered/resolved with no sequelae			
Recovered/resolved with sequelae			
Death			

\* Treatment-emergent AE is defined as any AE, regardless of relationship to study drug, which occur during AE collection period of study drug or an event already present that worsens in either intensity or relationship to study drug following exposure to Viaskin®.

Table 19B. Treatment-Emergent AEs (TEAEs)\* by Treatment Groups  
(Number of TEAE)

	All	Viaskin® milk	Placebo
Number of TEAEs			
Number of potentially drug-related TEAE			
Number of severity of TEAE			
Mild			
Moderate			
Severe			
Life-threatening			
Death			
Number of serious TEAE			
Number of TEAE leading to discontinuation			
Number of TEAE leading to death			
Number of TEAEs per subject			
0			
1			
2			
3 +			
Number of local TEAE			
Number of severity of local TEAE			
Mild			
Moderate			
Severe			
Life-threatening			
Death			
Outcome			
Unchanged			
Worsened			
Recovered/resolved with no sequelae			
Recovered/resolved with sequelae			
Death			

\* Treatment-emergent AE is defined as any AE, regardless of relationship to study drug, which occur during AE collection period of study drug or any event already present that worsens in either intensity or relationship to study drug following exposure to Viaskin®.

Table 20. Summary Statistics of Local Skin Reactions (Adverse Events)

	All	Viaskin® milk	Placebo	
Number of patients with reactions				
0				
1				
2				
3				
4				

Values will be expressed as frequency counts (percentages) unless indicated.

Table 21. Summary of Laboratory Abnormalities based on CTC Grade by Visit and Treatment Groups

	Viaskin®Milk				Placebo				
	Visit 1	Visit 8	Visit 10	Visit 16	Visit 1	Visit 8	Visit 10	Visit 16	
Hematology									
RBC Count									
WBC Count									
Hemoglobin									
Hematocrit									
Platelet Count									
Segmented Neutrophils									
Lymphocytes									
Monocytes									
Eosinophils									
Basophils									
Chemistry									
Total Protein									
Blood Urea Nitrogen									
Creatinine									
ALP									

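### Cheap improvement: split the by-arm AE, TEAE and local-skin-reaction tables by study period, because the Placebo column otherwise takes in open-label time on active patch

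*SAP*

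**What the plan says.** SAP 4.5.1 commits to by-arm summaries of adverse events. The number of children "who experienced at least one AE as well as the number of AEs will be summarized by system organ class and treatment group" (Tables 17A and 17B). Overall AE and TEAE summaries by arm follow in Tables 18, 19A and 19B. For Table 20, "The number of subjects with adverse events on local skin reactions will be summarized". The shells of Tables 18 to 20 have three columns (All, Viaskin milk, Placebo) and no period or visit axis. The shell bodies of Tables 16 and 17 are not legible in the text reviewed, so for those two I rely on SAP 4.5.1 and the table titles. Protocol 13.6.6.1 also asks only for summaries by treatment group.

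The collection window is long. Protocol 12.1 states: "AEs will be recorded from the time written screening informed consent is signed until the time of the End of Study visit". The SAP's TEAE definition covers events "which occur during AE collection period of study drug", which is not clearly tied to the first patch. Protocol Appendix 3 does tie it, to events "which occur during or after the initial Viaskin® application of study drug".

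After Visit 10 all children wear the active patch. Protocol 8.5.1 repeats the stepped wear time at that point, "in particular for subjects crossing over from placebo to the active Viaskin Milk treatment". Protocol 8.5.4 adds: "There will be no blinding of study medication during this part of the study".

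SAP 4.1 gives a column rule for efficacy: "Subjects in the ITT population will be categorized by their randomized treatment assignment". It gives none for the safety population, although it assigns that population to comparing safety between groups.

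**The concern.** The blinded randomised comparison ends at Visit 10. A table running from consent to End of Study mixes screening (including milk introduction before any patch), the blinded patch period, and an open-label period in which both arms receive the same product.

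The Placebo column then contains events on active patch. A former placebo child whose first local reaction comes in the open-label weeks counts in Table 20 as a placebo child with a reaction. The potentially drug-related rows do not repair this. They pool relatedness judged under blinding with relatedness judged when everyone knows the patch is active.

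At stake is whether the by-arm safety tables of a first proof-of-concept study show the patch's tolerability against placebo at its true size. The switch, which the protocol itself treats as a safety moment, also has no summary of its own.

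**Working it through.** The plan states no figure on this point, so there is none to reproduce. The check is one of layout plus exposure arithmetic.

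**Which column does an open-label event in a former placebo child fall in?** No sentence says so for AEs. But SAP Table 21 has a Placebo column at Visit 16, and Table 22 has Placebo columns at Visits 11 to 17. Nobody wears a placebo patch at those visits, so Placebo there can only mean randomised to placebo. Tables 9B and 13B (end of open label) follow the same convention. I apply it to Tables 17 to 20.

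**Exposure.** Inputs: 16 active and 6 placebo children (SAP 2.4.2); up to 11 months double-blind and 11 open-label (Protocol 8.3).

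- Placebo arm on placebo patch: 6 × 11 = 66 child-months.
- Placebo arm on open-label active patch: 6 × 11 = 66 child-months.
- Share on active patch: 66/132 = 50%. If 2 of 6 left at Visit 10 (an assumption), it would be 44/(66 + 44) = 40%.
- The collection window is at most about 3.5 + 22 + 0.5 = 26 months. The blinded comparison is 11/26 = 42% of it, and screening is 3.5/26 = 13%.

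**Events per child** (Tables 17B and 19B). Assume constant monthly rates, equal periods, no screening AEs, and a true active-to-placebo rate ratio R. With the placebo rate set to 1 per month, the active column shows 22R events per child and the Placebo column shows 11 + 11R. The apparent ratio is 22R/(11 + 11R) = 2R/(1 + R).

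| True R | Apparent ratio |
|---|---|
| 1.5 | 3/2.5 = 1.20 |
| 2 | 4/3 = 1.33 |
| 3 | 6/4 = 1.50 |

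**Children ever affected** (Tables 17A, 19A and 20). The formula above does not apply to these. Let a and p be a child's risk of at least one reaction per period on active and placebo patch. The documents give neither, so I assume a from 0.5 to 0.9 and p from 0.1 to 0.3.

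- Double-blind difference: a − p, which is 0.20 to 0.80 over that range.
- Whole study, periods independent: [1 − (1 − a)²] − [1 − (1 − p)(1 − a)]. For a = 0.5 and p = 0.1 this is 0.75 − 0.55 = 0.20, against 0.40 in the double-blind period. For a = 0.9 and p = 0.3 it is 0.99 − 0.93 = 0.06, against 0.60. Over the whole range it is 0.06 to 0.20.
- Whole study, if a child who reacts to the active patch does so in either period and every placebo reactor would also react to active: a − a = 0.

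Dilution therefore affects both kinds of table, by an amount that depends on unstated rates.

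**The case against.** The strongest reply is that this is a small pilot with no formal safety testing, and that timing is not lost. SAP 4.5.1 lists every AE with start date, stop date and causality, and SAP 4 notes that listings or graphs may be the most informative display at this size. The safety objective (Protocol 7.2, SAP 2.2.5) names no placebo comparison. Worsening EoE on the patch is watched during the trial: a stopping rule (Protocol 8.4.3.2), a study visit and possible reduced wear time (8.5.6), monthly calls (9.12.1) and DSMB review (13.6.8). SAP 4.4.2.6 describes time to symptoms after milk reintroduction by group. Finer splits also have a problem of their own: the blinded milk phase lasts 1 week to 2 months and can end when symptoms recur, so its length may depend on outcome.

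Most of this stands, and it limits the point to the planned summaries. It does not answer that point. The safety population is defined for comparing safety, the by-arm tables are what most readers will use, and the SAP already splits disposition by period and laboratory and vital-sign abnormalities by visit.

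Three stronger readings are tempting but not supported:

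- That columns might follow the patch received. The active column would then average (16 × 22 + 6 × 11)/22 = 19 months per child against 11 on placebo, and equal rates would show as 19/11 = 1.73. Tables 21 and 22 point the other way, so the gap is one unstated sentence.
- That the apparent ratio can never exceed 2. That limit comes from the constant-rate, equal-period assumptions. It is not a property of the tables.
- That leaving Visits 5 to 9 out of symptom Tables 10 and 11 is an error. The symptom endpoints are defined at 11 and 22 months, so a display of those visits would be an addition.

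**Conclusion.** The point holds as a low-cost improvement. As written, the by-arm AE, TEAE and skin-reaction tables pool screening, blinded and open-label time, and up to half of the placebo arm's treatment time in them is on active patch. Any true patch-related excess would look smaller than it was in the blinded comparison: a rate ratio of 2 would show as about 1.33 in events per child.

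That figure rests on the randomised-arm convention, full duration, constant rates, equal periods and no screening AEs. Wear time is stepped up at the start of each period, so constant rates are a simplification, and the figure does not carry over to tables that count children. The 50% share needs only the convention and full duration.

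A reader might infer that a safety signal would go unseen, or that the trial's conclusions are at risk. The documents do not support that: the dated listing and the monitoring rules remain, and the primary analysis is untouched. With 6 placebo children, even well-split tables can only describe.

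**What to change.** In SAP 4.5.1 and the shells of Tables 17 to 20:

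1. Present a double-blind table (first patch at Visit 4 to Visit 10), which is the by-arm comparison, and a separate open-label table (after Visit 10) with former placebo children in their own column. State where events fall on the Visit 10 day, and in the gap if the first open-label patch is postponed (up to 7 days).
2. List screening AEs apart, and count TEAEs from the first patch application, as Protocol Appendix 3 does.
3. State that columns in the safety tables are by randomised arm.
4. Give child-months of exposure for each column. At full duration these are 16 × 11 = 176 and 6 × 11 = 66 in each period.

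Two additions are optional. Double-blind events may be shown before and after the Visit 9 milk restart, with exposure time and a note that the milk phase can end because of symptoms. A descriptive by-arm display of symptom scores at Visits 5 to 9, without tests, may also be added.

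The cost is one period flag, a few sentences and revised shells. AE dates, visit dates and scores are already collected, and sample size, power and alpha do not change. The downside is a few extra descriptive tables with small cells.
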